7.7. Lost to Follow-Up

A participant will be considered lost to follow-up if the participant repeatedly fails to return for scheduled visits and if the trial site is not able to get in contact with the participant.

The following actions must be taken if a participant fails to return to the clinic for a required trial visit:

- The trial site must attempt to contact the participant and reschedule the missed visit as soon as possible, counsel the participant on the importance of maintaining the assigned visit schedule and ascertain whether or not the participant wishes to and/or should continue in the trial.
- Before a participant is deemed lost to follow-up, the Investigator or designee must make every effort to regain contact with the participant (where possible, 2 attempts of contact by telephone calls, and if necessary, a certified letter to the participant's last known mailing address or local equivalent methods). These contact attempts should be documented in the participant's medical record.
- Should the participant continue to be unreachable, the participant will be considered to have withdrawn from the trial.

8. TREATMENT OF PARTICIPANTS

8.1. Description of Investigational Product

Rademikibart drug product is provided as a colorless-to-pale yellow sterile solution at 150 mg/mL concentration in a 1 mL single-dose PFS that delivers 1.0 mL solution.

Placebo for rademikibart is provided as colorless-to-pale yellow sterile solution containing the same excipients as the rademikibart drug product in a 1 mL single-dose PFS that delivers 1.0 mL solution.

The IP will be administered by SC injection (see Section 9.4).

8.2. Concomitant Medications

All medications taken from 3 months prior to the participant's initial Screening Visit 1a or Visit 1b through the end of the trial, including those given in the urgent healthcare setting to treat the index acute COPD exacerbation, should be recorded in the participant's source document and in the eCRF.

Any medication or vaccine (including over-the-counter or prescription medicines, vitamins, and/or herbal supplements) that the participant is receiving at Screening Visits 1a and/or 1b or receives following Screening and throughout the trial must be recorded in the source documents and eCRF along with:

- Reason for use.
- Start and end date of administration.
- Dosage information including dose and frequency.

The Medical Monitor should be contacted if there are any questions regarding prior or concomitant medication or procedures.

8.2.1. Prohibited Concomitant Therapy

The concomitant treatments are not permitted during the Screening Period or the randomized Treatment Assessment Period are listed in [Table 3](#).

Table 3: Prohibited Therapy

Prohibited Medication/Therapy:	Usage:
Rescue medications other than salbutamol/albuterol or levosalbutamol/levalbuterol (for example, short-acting anticholinergics [eg, ipratropium bromide])	Not recommended during the trial period. In case of use in exceptional circumstances (eg, prescribed by a physician not participating in the trial or used for managing an COPD exacerbation event), their use will be documented in the participant's file and reported in the eCRF. Short-acting anticholinergics (eg, ipratropium bromide) for use as a rescue medication are not permitted from the Screening Visit 1b through completion of the trial, unless required for treatment of an acute COPD exacerbation.

Prohibited Medication/Therapy:	Usage:
Any marketed nonbiologic drug that modulates type 2 cytokines (eg, suplatast tosilate)	Not allowed 30 days or 5 half-lives (whichever is longer) prior to randomization, and throughout the trial.
Any marketed biologic (eg, dupilumab, or other monoclonal antibody) or investigational biologic treatment (including investigational use of an approved biologic)	Not allowed 16 weeks or 5 half-lives (whichever is longer) prior to randomization, throughout the trial until the Follow-up Visit Week 8.
Any investigational nonbiological drug or treatment (including investigational use of an approved drug)	Not allowed 30 days prior or 5 half-lives (whichever is longer) to randomization, and throughout the trial.
Live attenuated vaccines (see Appendix I)	Not allowed 4 weeks prior to randomization, and during the trial including the Follow-up Period.
Any immunomodulators or immunosuppressives (except for short term usage of oral corticosteroids for COPD exacerbation or topical/nasal corticosteroids)	Not allowed 12 weeks or at least 5 half-lives (whichever is longer) prior to randomization, and throughout the trial.
PDE4 inhibitors (roflumilast)	Use of PDE4 inhibitors (eg, roflumilast) from Screening throughout the trial, unless on stable therapy for >12 months prior to Screening Visit.
Macrolide antibiotics (eg, azithromycin)	Not allowed for chronic use from Screening throughout the trial, unless on stable therapy for >12 months, with the exception of prior treatment for a COPD exacerbation. If treatment duration is expected to exceed 14 days, the Sponsor Medical Monitor must be contacted.
Intravenous immunoglobulin therapy or blood products	Not allowed 30 days prior to randomization, and throughout the trial.

COPD = chronic obstructive pulmonary disease; eCRF = electronic case report form; PDE = phosphodiesterase.

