4.4.3. Protocol Deviations

A protocol deviation is any modification to protocol-specified procedures, whether intentional or not, that occur without prior IRB/IEC approval and submission to regulatory authority(ies) of the protocol amendment implementing the modification. The Investigator will not implement any protocol modification without prior approval of the IRB/IEC and agreement by the Sponsor except where necessary to eliminate an apparent immediate hazard to trial participants.

Protocol deviations fall into 2 categories:

- Important Protocol Deviations.
- Other Protocol Deviations.

Important Protocol Deviations are deviations that might significantly affect the completeness, accuracy, and/or reliability of the trial data or that might significantly affect a participant's rights, safety, or well-being. Some examples include:

- Failure to conduct trial procedures designed to assess participant safety or failure to adequately monitor participants.
- Administration of concomitant treatment prohibited by the protocol that may increase risks to participants and/or impact interpretation of safety and efficacy.
- Failure to obtain informed consent or meet other applicable requirements for the protection of human participants.
- Failure to protect a participant's identifiable private protected health information.

- Enrollment of a participant in violation of key eligibility criteria designed to ensure a specific participant population.
- Failure to administer the IP according to specifications in the protocol, administration of the wrong treatment or incorrect dose to participants.
- Failure to collect data to evaluate important trial endpoints (eg, primary or secondary endpoints).
- Premature unblinding of a participant's treatment allocation for reasons other than those specified in the protocol.
- Failure to withdraw IP administration from participants who meet withdrawal criteria.

Other Protocol Deviations are those that do not meet the definition of an Important Protocol Deviation. Some examples of all Other Protocol Deviations include small deviations from protocol-specified visit windows; a signed consent missing a participant's initials on a page; or failure to perform a trial procedure not relevant for safety monitoring or not related to an important trial efficacy endpoint (eg, primary or secondary endpoints).

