7.1. Inclusion Criteria

Participants are eligible to be included in the trial only if ALL of the following criteria apply:

1. Written informed consent obtained prior to performing any protocol-related procedures.
2. Adults (40 to 80 years, inclusive) at the time of signing the informed consent.
3. Body weight of ≥ 45 kg and body mass index within the range 16 to 35 kg/m² (inclusive) at Screening.
4. Physician-diagnosed COPD with duration of ≥ 12 months by medical chart or participant report.
5. Must have experienced at least 1 COPD exacerbation requiring the use of systemic corticosteroids (oral or parenteral) within the previous 12 months prior to Screening.
6. Participants who consent to participate in the trial while in a stable condition must have current or historic evidence of spirometry confirming airflow obstruction (post-BD FEV₁/FVC $\leq 70\%$) and a documented historical peripheral blood eosinophil count of ≥ 250 cells/ μ L and/or a FeNO ≥ 25 ppb within 12 months prior to Screening Visit 1a.
7. Current or former smoker with a history of smoking of ≥ 10 pack-years.

Note: This includes tobacco, marijuana, and vaping products.

8. In the opinion of the Investigator, participant is willing and able to comply with all trial visits and trial-related procedures (such as, willing and able to perform entries of daily electronic diary [e-diary] patient-reported outcomes [PRO]s).
9. Women of childbearing potential, unless surgically sterile (including tubal ligation) and/or at least 2 years postmenopausal, should have a confirmed negative serum beta-human chorionic gonadotropin (β -hCG) test at Screening Visits 1a and/or 1b and agree to use a highly effective method of avoiding pregnancy from trial recruitment through Day 56, see [Appendix B](#).

Note: A female is considered of childbearing potential following menarche and until becoming postmenopausal unless permanently sterile. Permanent sterilization methods include hysterectomy, bilateral salpingectomy and bilateral oophorectomy.

Additional Inclusion Criteria for Current Acute COPD Exacerbation:

10. Current acute COPD exacerbation requiring an urgent healthcare visit for treatment.

Note: COPD acute exacerbation is defined as an acute increase in symptoms (1 or more of the following: cough frequency and severity, sputum production, dyspnea) beyond normal day-to-day variations leading to a change in medication.

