For the purposes of this trial, an urgent healthcare setting may include an ED, a hospital inpatient ward, an urgent healthcare facility, or a clinic affiliated with or in close proximity to a hospital/ED/urgent care equipped to provide the level of care specified in this protocol. The primary reason for ED visit, urgent healthcare visit, or hospitalization is for acute COPD exacerbation.

11. Peripheral blood eosinophil count of ≥ 300 cells/ μ L at Screening Visit 1b or as part of the assessment of the index acute COPD exacerbation within 72 hours prior to Screening Visit 1b.

Note: Where possible, it is advisable to obtain eosinophil count prior to the administration of corticosteroids.

12. Requires systemic corticosteroids as SoC treatment in the urgent healthcare setting for the current acute COPD exacerbation.

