8.2.2. Permitted Concomitant Therapy

8.2.2.1. COPD Medications and Non-Drug Therapies

To be eligible to be randomized in this trial, participants must present with an acute COPD exacerbation characterized by an eosinophilic phenotype and required systemic corticosteroids as SoC treatment in the urgent healthcare setting for the acute exacerbation. SoC for the index acute exacerbation is defined for this protocol as treatment with oral/systemic corticosteroid[s] (40 mg/day prednisone or equivalent) for 5 days with or without antibiotic(s) for 7 days; the modification of the dose and/or duration of prednisone (40 mg/day or equivalent) and/or the antibiotic is not recommended but may be allowed according to the Investigator's/medically qualified designee's judgement.

The start of SoC is defined as the start of either oral or systemic corticosteroids(s) or antibiotic(s), whichever is earliest.

Note: SoC must be documented in the participant's source documentation and in the eCRF. The use of other medications for treatment of the index acute COPD exacerbation and any subsequent COPD exacerbation(s), if applicable, is at the discretion of the Investigator or medically qualified health care personnel. Use of medication for treatment of subsequent exacerbations does not need to follow the SoC requirements for the index acute exacerbation.

In addition, participants are instructed to continue their regular COPD maintenance treatments (eg, LAMAs, LABA/ICS combinations, LABA/LAMA combinations, or LABA/LAMA/ICS combinations) for the duration of the trial. However, participants must withhold the morning dose of usual scheduled COPD medications on the morning of the spirometry assessments, except when treatment is needed for an acute COPD exacerbation.

Note: Modification(s) of the dosing regimen for the regular COPD maintenance treatments is(are) permitted as deemed medically appropriate by the Investigator/medically qualified designee; the modifications will be recorded in source documents and eCRF.

Other concomitant COPD maintenance medications may be allowed at the discretion of the Investigator following consultation with the Sponsor Medical Monitor, with the exception of short-acting anticholinergics for use as rescue medication.

Oxygen for intermittent use or PRN therapy ≤ 15 hours per day is allowed. LTOT or nocturnal oxygen therapy required for >15 hours is excluded throughout the trial.

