13.3. Analysis Sets

For the purposes of analysis, the following analysis sets are defined:

Analysis Set	Description
RS	All participants who are randomized to treatment.
FAS	All participants from RS having taken at least 1 dose of IP after randomization; data will be presented based on randomized treatment group.
PPS	All participants from FAS without important protocol deviation(s) that could affect the evaluation of the IP.
SS	All participants from RS having taken at least 1 dose of IP after randomization; data will be presented based on treatment actually received.
PKS	All participants from RS with at least 1 dose of rademikibart taken and with at least 1 post-dose evaluable PK blood sample.

FAS = Full Analysis Set; IP = investigational product; PKS = Pharmacokinetics Analysis Set; PPS = Per-Protocol Set; RS = Randomized Set; SS = Safety Analysis Set

All screened participants will be accounted for in the clinical study report (CSR). The inclusion and/or exclusion of participants from the trial analysis sets will be documented in the SAP before breaking the randomization code.

Participants in the Randomized Set (RS) will be summarized according to the treatment group to which they were randomized.

Participants in the Full Analysis Set (FAS) will be summarized according to the treatment group to which they were randomized, regardless of treatment received. The primary analyses of all efficacy endpoints will be conducted in the FAS.

Supportive efficacy analyses will be conducted in the Per-Protocol Set (PPS). Analyses based on the PPS will be performed to support the results obtained for the FAS. Reasons for exclusion from the PPS will be documented prior to database lock and unblinding.

The analysis population for the safety endpoints will be the Safety Analysis Set (SS). These participants will be analyzed according to their actual treatment received, regardless of the randomized treatment assigned.

The analysis population for the immunogenicity endpoints will be the subset of Pharmacokinetic Analysis Set (PKS) population with at least a predose (baseline) and at least one evaluable post-dose immunogenicity assessment.

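### Table 3 exempts only oral (and topical/nasal) corticosteroids from the immunosuppressive ban, while the eligibility and standard-of-care text speaks of systemic corticosteroids; read literally, a parenteral course is both accepted and prohibited

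*Protocol*

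**What the plan says.** Protocol Section 8.2.1, Table 3, has a row for any immunomodulator or immunosuppressive. Its window is "Not allowed 12 weeks or at least 5 half-lives (whichever is longer) prior to randomization, and throughout the trial". The exemption in that row reads "except for short term usage of oral corticosteroids for COPD exacerbation or topical/nasal corticosteroids". The parenteral route is not named.

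The eligibility and treatment sections use a wider term:

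- Section 7.1, inclusion 12: "Requires systemic corticosteroids as SoC treatment in the urgent healthcare setting for the current acute COPD exacerbation".
- Section 8.2.2.1, under permitted therapy: "SoC for the index acute exacerbation is defined for this protocol as treatment with oral/systemic corticosteroid[s] (40 mg/day prednisone or equivalent) for 5 days". The same section dates the start of standard of care (SoC) from an oral or systemic corticosteroid or an antibiotic, and it does not bind treatment of later exacerbations to the index SoC requirements.
- Section 7.1, inclusion 5, shows what systemic covers when it describes qualifying history: "systemic corticosteroids (oral or parenteral) within the previous 12 months prior to Screening".

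Two further places link prohibited therapy to the analysis. Section 4.4.3 gives as an example of an Important Protocol Deviation "Administration of concomitant treatment prohibited by the protocol that may increase risks to participants and/or impact interpretation of safety and efficacy". Section 13.3 defines the PPS as "All participants from FAS without important protocol deviation(s) that could affect the evaluation of the IP".

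**The concern.** Every participant must require a systemic corticosteroid to enter the trial, so the conflict concerns the one background treatment common to all. A site that follows Section 8.2.2.1 would record a parenteral course as SoC. A site or monitor that follows Table 3 could record the same course as prohibited therapy. With approximately 50 sites planned, including emergency departments and inpatient wards, deviation coding could differ between sites for no clinical reason.

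The statistical stake is the PPS, on which the primary analysis (Section 13.4.5.2) and the key secondary analysis (Section 13.4.6.1) are repeated. Section 10.1 counts a second course of systemic steroids as treatment failure. If failures re-treated parenterally were removed and those re-treated orally kept, the PPS would be selected on the primary outcome. If the drug works, the placebo arm would lose more participants. Documenting exclusions before unblinding does not remove that dependence on outcome.

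**Working it through.** **Step 1: the texts side by side.**

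| Situation | Section 7.1 and 8.2.2.1 | Table 3, read literally |
|---|---|---|
| Oral course, index event | Required or permitted | Exempt |
| Parenteral course, index event | Within systemic, so required or permitted | Not exempt |
| Parenteral course, later exacerbation | Left to the investigator | Not exempt |

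Corticosteroids do fall within the banned class as the protocol uses it. Exclusion 2 lists regular prednisolone and hydrocortisone as immunosuppressives, and the row would need no corticosteroid exemption otherwise. No statement gives Section 8.2.2.1 precedence over Table 3.

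**Step 2: the protocol's own figure.** Section 13.2 assumes failure rates of 22.5% and 45%, 152 evaluable participants (76 per arm), two-sided 5%, and at least 80% power. With the pooled normal approximation:

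- mean rate = (0.225 + 0.45)/2 = 0.3375
- SE under the null = √(2 × 0.3375 × 0.6625/76) = 0.0767
- SE under the alternative = √((0.225 × 0.775 + 0.45 × 0.55)/76) = 0.0745
- power = Φ((0.225 − 1.96 × 0.0767)/0.0745) = Φ(1.00) = 84.2%

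152/0.95 = 160. The stated size reproduces (a continuity-corrected version gives 79.5%, close to 80%). The wording conflict does not enter this calculation.

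**Step 3: parenteral use for the index event.** The protocol gives no share for parenteral use, so these shares are assumptions. If a share q of participants were excluded from the PPS independently of arm and outcome, n per arm = 76 × (1 − q):

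| q | n per arm | PPS power |
|---|---|---|
| 10% | 68.4 | 80.2% |
| 25% | 57.0 | 72.5% |
| 50% | 38.0 | 54.7% |

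This costs precision but does not bias the difference.

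**Step 4: parenteral re-treatment after randomization.** If a share f of failures is dropped from each arm, the PPS rate becomes p(1 − f)/(1 − fp). The values of f are again assumptions.

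| f | Rademikibart | Placebo | Difference |
|---|---|---|---|
| 0 | 22.5% | 45.0% | 22.5 points |
| 10% | 0.2025/0.9775 = 20.7% | 0.405/0.955 = 42.4% | 21.7 points |
| 25% | 0.16875/0.94375 = 17.9% | 0.3375/0.8875 = 38.0% | 20.1 points |
| 50% | 0.1125/0.8875 = 12.7% | 0.225/0.775 = 29.0% | 16.4 points |

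Here the estimate itself moves, and toward no difference. If no such use is classed as a PPS-relevant deviation, f = 0 and nothing changes.

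**The case against.** The strongest reply is that the protocol should be read as a whole. Section 8.2.2.1 is the specific permission for exacerbation treatment, Table 3 is a general row, and Section 8.2 refers medication questions to the Medical Monitor. Exclusion 31 also says oral corticosteroids, which suggests loose drafting rather than an intended ban by route. This is a sensible reading and probably the intended one, but the text does not state it.

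The reply on the PPS is stronger. Two judgements stand between Table 3 and exclusion. Section 4.4.3 counts prohibited treatment as important only if it may raise risk or affect interpretation. Section 13.3 removes only important deviations that could affect evaluation of the product, with reasons documented before lock and unblinding. Classing required SoC that way would be strained. This stands: exclusion is possible on the text but not automatic.

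A reader might infer more than the documents support:

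- **That parenteral courses are prohibited and the PPS is distorted.** The first holds only on a literal reading of one cell, and the second only if both judgements go that way.
- **That Section 7.5.1, item 6 (need for prohibited medication), would force discontinuation.** The product is a single Day 0 dose, so after dosing there is nothing left to stop.
- **That maintenance inhaled corticosteroids are banned because Table 3 omits them.** Nothing classes them as immunosuppressives, and Section 8.2.2.1 tells participants to continue them.
- **That a number of affected participants can be given.** The protocol has no figure for parenteral use.

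**Conclusion.** The inconsistency is real: Table 3's oral-only exemption and the systemic wording of inclusion 12 and Section 8.2.2.1 cannot both be applied literally to a parenteral course. The effect on the analysis is conditional and confined to a supportive set. Under the protocol's assumed failure rates, and with an assumed 10% to 50% of failures dropped equally from both arms, the PPS risk difference would fall from 22.5 to between 21.7 and 16.4 points. It would not change at all if nobody treats such use as an important deviation affecting evaluation of the product. The primary analysis in the Full Analysis Set, the sample size of 160 and the two-sided 5% level are not affected. Severity is minor: a wording conflict worth removing because it concerns treatment that every participant must require.

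**What to change.** Reconcile the Table 3 row with inclusion 12 and Section 8.2.2.1, so that the same corticosteroid use is not required or permitted in one place and prohibited in another. Carry the agreed wording into the matching Synopsis text. Which route or routes the reconciled text allows is for the sponsor's clinical team; this review takes no position.

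Then add one sentence to Section 13.3: corticosteroid use permitted under the reconciled text is not by itself a reason for exclusion from the PPS. This closes the outcome-dependent exclusion whichever way the texts are aligned.

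The cost is the aligned wording (one table cell if Table 3 is the text that changes) and one sentence. Data collection, sample size and the primary analysis stay as they are.
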